8.2.13 MRI (with AMRA Profiler)

A semi-automated cloud-based image analysis tool, AMRA Profiler, optimizes MR images to fully analyze entire body compartments, and provide precise body composition measurements. AMRA Profiler uses quantitative fat and water separation to integrate the total fat signal intensity in a compartment of interest; and provide a three-dimensional approach to improve the robustness of the segmentation. This system is quick, cost effective, validated, and reproducible. The automated single scan computes multiple measurements, and is completed in six minutes using fewer coils, no radiation, or contrast. MRI scans with body composition analysis will be performed before the bariatric embolization procedure, and four times over 12 months after the procedure, at weeks 4, and months 3, 6, and 12. A standard 1.5T or 3T scanner with AMRA Profiler will be used to quantify visceral adipose tissue (VAT), abdominal subcutaneous adipose tissue (ASAT), thigh muscle volume, proton-density liver fat fraction, total adipose tissue volume (TAT), total lean tissue volume (TLT), muscle group volumes, intramuscular adipose tissue (IMAT), and individual muscle volumes. The data will be analyzed in conjunction with weight and HbA1c in order to see what patients will be suitable in the future for this procedure to determine which participants are suited and will benefit most from this procedure. As possible characterization of fat will be performed. In addition to the MRI with AMRA Profiler, the scan will also include Siemens work-in-progress sequences for evaluating fatty acid composition. Overall, the MRI is expected to take 30-38 min per session.

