1.0 Introduction

This document provides details of the statistical considerations, analyses, and reports planned for the Bariatric Embolization of ArTeries with imaging visibLe EmbolicS (BEATLES) trial. BEATLES is an investigator-initiated, prospective, double-blinded, randomized, sham-controlled study that will assess the impact of bariatric embolization on the systemic levels of obesity-related hormones and, as a consequence, on weight loss. The goal of this study is to help treat obesity combining a lifestyle program and a minimally invasive, angiographic approach.

All data collection procedures and statistical analyses in this SAP report are considered as final, and were finalized and approved by the Clinical Investigators and Sponsor prior to data lock. In addition, the data collection procedures and statistical analyses detailed in this SAP report may modify and are given precedence over the analytical plans outlined in the clinical protocol; however, any major modifications or change in the primary endpoint and/or its analysis will also be reflected in a protocol amendment.

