3.5 Outcome Measures

Primary Efficacy Endpoint

The primary outcome is the change in body weight at 12 months' post-procedure from baseline weight.

Secondary Efficacy Endpoints

Secondary efficacy endpoints include the following: 1) Percent change in body weight at 12 months' post-procedure from baseline; 2) The achievement of > 5% reduction in body weight at 12 months' post-procedure; 3) Percent excessive weight loss (EWL) at 12 months' post-procedure from baseline; and 4) Change in MRI biomarkers liver fat proton

density fat fraction (PDFF), visceral adipose tissue volume, subcutaneous adipose tissue volume, and muscle fat infiltration.

Primary Safety Outcome

The total adverse events (AEs) from procedure to 12 months' post-procedure will be used to assess the safety of the BAE procedure and the use of radiopaque 100-200 μm microspheres in obese patients.

Secondary Safety Outcome

The total number of events until day 30 post-procedure will be considered the secondary safety outcome.

Exploratory Outcomes

The following outcomes will be considered as exploratory and potentially supportive of future research studies: 1) Change in blood pressure; 2) Change in lipid/lipoprotein profiles; 3) Change in obesity related hormones (ghrelin, LEAP2, leptin, glucagon-like peptide-1, peptide YY, etc.); 4) Changes in markers of obesity-related complications; 5) Food intake; 6) Hungry and satiety measures; 7) Quality of life as measured by the SF-36 and IWQOL; 8) Endoscopy results; 9) Ghrelin expression in pre- and post-operative fundal biopsy samples; 10) Changes in taste perception; 11) Image analyses of bead distribution and fundal coverage; 12) Embolization endpoints of occlusion and recanalization; 13) Change in muscle volume; 14) Change in muscle fat infiltration; 15) Change in visceral adipose tissue; 16) Change in CHD propensity; 17) Change in DT2 propensity; and 18) Differing treatment response in patients with adverse muscle composition.

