5.5 Analysis of Secondary Efficacy Measures

Statistical assessments of the change in the continuous body-mass measures at 12-months from baseline (e.g. percent body-fat, excess weight loss) will follow the analyses described above for the primary efficacy measure. The binary outcome of > 5% weight loss will be statistically compared by treatment arm using the chi-square goodness-of-fit-test. Risk differences and relative risks, along with corresponding 95% confidence intervals, will be also calculated to quantify this group difference.

[How do we analyze the change in the multi-compartment composition?]

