5.9 Multiplicity

The primary analysis of efficacy is tested at the two-sided alpha level of 0.20. In addition, secondary analyses will consider the alpha = 0.20 two-sided type I error. Secondary analyses will be examined in the order specified, and will not be corrected for multiplicity of testing. For safety outcomes, multiplicity will not be considered since this study is not powered on safety.

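### The SAP, declared final, leaves an open author question where the MRI secondary endpoint's analysis should be; its timepoint is missing and its tier and scan schedule are inconsistent

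*SAP*

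**What the plan says.** **Status.** SAP 1.0 states: "All data collection procedures and statistical analyses in this SAP report are considered as final". It also gives the SAP precedence over the protocol's analysis plan.

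**Method.** SAP 5.5 sends "Statistical assessments of the change in the continuous body-mass measures at 12-months from baseline (e.g. percent body-fat, excess weight loss") to the primary-endpoint methods and gives a chi-square test for the >5% responder endpoint. It then asks, in brackets, "How do we analyze the change in the multi-compartment composition". No answer follows. Protocol 9.4.3 lists the MRI endpoint but gives a method only for the responder endpoint.

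**Definition and tier.** In SAP 3.5, secondary efficacy items 1 to 3 are each fixed at 12 months. Item 4 covers liver fat fraction, "visceral adipose tissue volume, subcutaneous adipose tissue volume, and muscle fat infiltration", with no timepoint. The exploratory list in the same section includes "14) Change in muscle fat infiltration; 15) Change in visceral adipose tissue".

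**Schedule.** Protocol 8.2.13 plans MRI before the procedure and "four times over 12 months after the procedure, at weeks 4, and months 3, 6, and 12". The Schedule of Activities (Protocol 1.3) marks MRI before the procedure and at months 3, 6 and 12, with the 4-week cell empty. The payment table in Protocol 5.5 pays for MRI only from months 3-5 onward.

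**Error control.** SAP 5.9 says "secondary analyses will consider the alpha = 0.20 two-sided type I error" and that these analyses "will not be corrected for multiplicity of testing". It adds that they are taken in their listed order, but gives no stopping rule.

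**The concern.** A reader cannot tell from the SAP which test will be applied to the MRI data, at which visit, or whether visceral fat and muscle fat infiltration count as secondary or exploratory. If these choices are made after the data are seen, a reported MRI difference has no clear error rate. Protocol section 3 says the endpoint should inform patient selection for future trials, and Protocol 8.2.13 says the MRI data will help show who benefits most. The schedule conflict is also practical: a site cannot both perform and omit a week-4 scan.

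**Working it through.** **1. The plan's own figure.** The documents give no familywise error for the MRI endpoint. The nearest stated figure is the primary sample size (SAP 3.8), which uses the same alpha of 0.20. The difference is 8 − 3.3 = 4.7 kg and the SD is 7 kg. Two-sample t power at two-sided 0.20 is 0.794 with 20 per arm and 0.809 with 21, so 21 per arm for 80% power is reproduced. Dropout: 21 / 0.8 = 26.25, rounded up to 27, as stated. The sample size is not in question here.

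**2. Inputs for the MRI endpoint.**
- Number of biomarkers: 4 (SAP 3.5, secondary item 4).
- Alpha per test: 0.20 two-sided, uncorrected (SAP 5.9).
- Visits tested: one, month 12. This is an assumption, by analogy with items 1 to 3.
- True effect: none on any biomarker (the null case).
- Correlation ρ between the four test statistics: not in the documents, so varied from 0 to 0.8.

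**3. Independent tests.**
- Either direction: 1 − (1 − 0.20)^4 = 1 − 0.4096 = 0.590.
- Favouring embolization only, 0.10 per test: 1 − 0.90^4 = 1 − 0.6561 = 0.344.
- Expected number of false positives, whatever the correlation: 4 × 0.20 = 0.8.

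**4. Correlated tests.** For four standard normal statistics with common correlation ρ and cut-off c = 1.2816 (the 90th normal percentile):

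P(at least one) = 1 − ∫ φ(u) [Φ((c − √ρ·u)/√(1−ρ)) − Φ((−c − √ρ·u)/√(1−ρ))]^4 du.

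For one direction, the second Φ term is dropped.

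| ρ | Either direction | Favouring embolization |
|---|---|---|
| 0 | 0.590 | 0.344 |
| 0.3 | 0.560 | 0.295 |
| 0.5 | 0.510 | 0.259 |
| 0.6 | 0.475 | 0.239 |
| 0.7 | 0.434 | 0.217 |
| 0.8 | 0.386 | 0.193 |

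The either-direction figure crosses 0.50 at ρ of about 0.53. Simulated two-sample t-tests agree: with 21 per arm, 0.592 at ρ = 0 and 0.515 at ρ = 0.5; with 27 per arm, 0.592 and 0.512.

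**5. Effect of a simple correction.** Bonferroni would test each biomarker at 0.20 / 4 = 0.05. If independent, the familywise error is then 1 − 0.95^4 = 0.185, and it cannot exceed 0.20.

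**6. The textual gaps need no arithmetic.** Two of the four biomarkers (visceral fat and muscle fat infiltration) appear in both tiers of SAP 3.5. Protocol 8.2.13 has four post-procedure scans and the Schedule of Activities has three.

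**The case against.** **A default exists.** SAP 5.5 already applies the primary methods at 12 months to continuous body-mass measures, and items 1 to 3 of the secondary list are at 12 months. This stands in part: 12 months is the natural reading, and it is why the working uses one visit. But the sentence names percent body-fat and excess weight loss, neither of which is one of the four biomarkers, and the query that follows shows the authors had not settled the matter.

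**No correction is a disclosed choice.** SAP 5.9 says so openly, for a phase 2 trial. This stands. Each test keeps its nominal 0.20 error, and analysts working with A/B labels (SAP 3.3) have less scope to select by direction. What is missing is the size of the joint error. The listed order does not limit it: there is no stopping rule, and no order is set among the four biomarkers.

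**Stronger readings that the documents do not support.** A reader might infer that a false-positive MRI finding is more likely than not. At one visit that requires no true effect on any biomarker, four separate tests, results in either direction counted, and a common correlation below about 0.53. Fat measures in the same patients may well be correlated more strongly than that. A reader might also multiply biomarkers by visits: 12 tests give 1 − 0.8^12 = 0.93 and 16 give 1 − 0.8^16 = 0.97. The missing timepoint permits such testing but the SAP does not plan it, independence is least credible across repeat scans of one patient, and 16 tests would need the disputed week-4 scan.

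**Conclusion.** The point holds. The MRI secondary endpoint has no specified analysis or timepoint, half of its biomarkers sit in two tiers, and the protocol contradicts itself on the week-4 scan. None of this depends on a probability.

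The statistical consequence is moderate. For four uncorrected tests at 12 months with no true effect, the either-direction familywise error is about 0.39 to 0.59 as the assumed common correlation falls from 0.8 to 0. Favouring embolization, it is about 0.19 to 0.34. Even the low end of the either-direction range is nearly twice the nominal 0.20.

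The defects are separate. A reader might take the bracketed question as the source of them all, but the missing timepoint and the double listing come from SAP 3.5, and the schedule conflict lies within the protocol. Answering the question alone would leave them in place. Nor should the endpoint be read as the trial's test of mechanism: Protocol section 3 gives that role to the obesity-related hormones, which are exploratory.

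**What to change.** 1. **SAP 5.5.** Replace the bracketed question with, for example: *For each of the four MRI biomarkers in section 3.5, change from baseline to 12 months will be compared between arms by ANCOVA, with the biomarker's own baseline value and diabetic status as covariates. Earlier visits will be reported as estimated differences with confidence intervals.* Diabetic status is the stratification factor (SAP 3.2). SAP 5.3 offers a t-test first, then an ANCOVA on whichever covariates look imbalanced; naming the covariates in advance removes that choice. If r is the correlation between baseline and 12-month values and their variances are equal, the large-sample variance of the ANCOVA estimate is (1 + r)/2 times that of the change-score t-test, so never larger. The cost is two degrees of freedom: with 21 per arm, 42 − 2 = 40 becomes 42 − 4 = 38.
2. **SAP 3.5.** Add the 12-month timepoint to item 4, and delete visceral adipose tissue and muscle fat infiltration from the exploratory list so that each biomarker has one tier.
3. **SAP 5.9.** State the familywise error for the four MRI tests beside the uncorrected results. If the sponsor prefers, name one lead biomarker for the 0.20 test instead. That is a matter of judgement, given the stated no-correction policy.
4. **Protocol.** Reconcile the week-4 MRI between section 8.2.13 and the Schedule of Activities, and check the payment table against the result.

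The cost is one SAP paragraph, two small SAP edits and a one-line protocol correction, with no change to sample size. The sponsor commits to a method and a visit before seeing the data.

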5.6 Analyses of Exploratory Measures

Several exploratory endpoints will be considered in the proposed trial as stated above, including blood pressure values, lipid profiles, serum obesity hormones, food intake, hunger assessments, QoL measures, and changes in taste perception. These endpoints will be quantified using a variety of assessment tools with both continuous and categorical scores. Statistical differences by treatment in these assessments will include the two-sample t-tests for continuous scores that are normally distributed, or the non-parametric Wilcoxon Rank Sum test for non-normally distributed continuous scores, while the binary and categorical scores will be analyzed using the Chi-Square goodness-of-fit test.

5.7 Sub-group Analyses

All analyses on the primary, secondary, and safety measures will be performed by gender, race, and ethnicity to determine if the treatment effect or safety differs by these important

demographic groups. Patient-specific clinical or “severity” factors/categories and treatment categories will also be explored. Planned explorations include diabetic status, age, compliance with weight management, baseline ghrelin levels, and post-procedure imaging characteristics.

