9.4.7 SUB-GROUP ANALYSES

All primary, secondary, and safety analyses will be performed by gender, race, and ethnicity to determine if the treatment effect or safety differs by these demographics. Patient-specific clinical or “severity” factors/categories and treatment categories will be explored. Planned explorations include diabetic status, age, compliance with weight management, baseline ghrelin levels, and post-procedure imaging characteristics.

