5.3 Analysis of the Primary Efficacy Measure

The primary efficacy outcome for the proposed trial is total weight loss from baseline weight at 12-months post-randomization. Differences in the weight loss from baseline between the treatment arms will be compared using the two-sample t-test. In addition, we will also consider an ANCOVA model that looks at the group difference in mean weight loss from baseline, adjusting for baseline covariates that might be imbalanced by treatment arm. We will use the Wilcoxon Rank Sum test to compare the two treatment arms if the data are found to be non-normal as determined by exploratory plots.

[1]

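### The plan asks whether the effect differs by gender, race and ethnicity, but only repeats between-arm analyses within subgroups and names no treatment-by-subgroup comparison

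*SAP*

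**What the plan says.** SAP 5.7 states that all analyses of the primary, secondary and safety measures "will be performed by gender, race, and ethnicity to determine if the treatment effect or safety differs by these" groups. Protocol 9.4.7 gives the same purpose: "to determine if the treatment effect or safety differs by these demographics".

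The analyses to be repeated are set out in SAP 5.3 to 5.5.
- For weight change, differences "between the treatment arms will be compared using the two-sample t-test", with a Wilcoxon test if the data are non-normal. The other continuous measures follow the same approach.
- The only regression model is an ANCOVA for the arm difference, "adjusting for baseline covariates that might be imbalanced by treatment arm". It has no treatment-by-subgroup term.
- The arms are compared on >5% weight loss with a chi-square test, plus risk differences and relative risks with 95% confidence intervals.
- For safety, SAP 5.4 speaks of differences in adverse events and names no method.

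SAP 5.9 says: "The primary analysis of efficacy is tested at the two-sided alpha level of 0.20". It adds that "secondary analyses will consider the alpha = 0.20 two-sided type I error" and that these "will not be corrected for multiplicity of testing". It does not mention subgroup analyses. Neither document gives the levels of race or ethnicity, or the expected share of patients in any subgroup.

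**The concern.** Whether an effect differs between subgroups is a question about the difference between two treatment effects. A between-arm test inside each subgroup asks whether the effect is zero there. Two such tests can give different verdicts when the effects are the same, because the subgroups are small or of unequal size. They can also agree when the effects differ. A method for the stated question exists and is inexpensive, so this is more than a missing detail.

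At stake is a reported sex, race or ethnicity difference that is only noise, or a claim of consistency that the data cannot support. The primary comparison of the two arms is not affected.

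**Working it through.** **Inputs.** SAP 3.8 and protocol 9.2 give mean losses of 8 kg and 3.3 kg (difference 4.7 kg), a common SD of 7 kg, two-sided alpha 0.20, and 21 evaluable per arm out of 27 randomised. SAP 3.1 gives 1:1 allocation. The subgroup splits below are assumptions, with equal numbers in the two arms.

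**The plan's own figure.** Two-sample t-test power comes from the noncentral t distribution with 2n − 2 degrees of freedom and noncentrality 4.7 / (7√(2/n)). At n = 21 the noncentrality is 4.7 / 2.16 = 2.18 and power is 80.9%. At n = 20 power is 79.4%. So 21 per arm is right, and 21 / 0.8 = 26.25 rounds up to 27.

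**Disagreement between subgroup verdicts.** Take a two-level factor with the same true effect in both levels, and let p1 and p2 be the within-subgroup powers at alpha 0.20. The chance that exactly one level is significant is p1(1 − p2) + p2(1 − p1).

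| Patients per arm in the two levels | p1, p2 at 4.7 kg | Disagree, 4.7 kg | Disagree, 2.35 kg |
|---|---|---|---|
| 11 / 10 | 0.605, 0.576 | 48% | 43% |
| 15 / 6 | 0.703, 0.442 | 52% | 44% |
| 17 / 4 | 0.743, 0.360 | 57% | 44% |

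First row: 0.605 × 0.424 + 0.576 × 0.395 = 0.484.

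With no treatment effect in either level, the chance is 2 × 0.2 × 0.8 = 32% for any split. If all 27 per arm are analysed (14 / 13), the powers are 0.681 and 0.657 and the disagreement at 4.7 kg is 44%. A simulation of 40,000 trials per setting gave 49%, 52% and 57% for the three table rows at 4.7 kg.

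**Other alpha.** If subgroup tests used 0.05, disagreement at 4.7 kg would be 43% (11 / 10) to 45% (15 / 6). With no effect it would be 2 × 0.05 × 0.95 = 9.5%.

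**More levels.** For a three-level factor with no effect, the chance of mixed verdicts is 1 − 0.2³ − 0.8³ = 48%.

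**An interaction test on the same data.** In the same simulations, a treatment-by-subgroup t-test found a false difference in 19.6-20.3% of trials at alpha 0.20 and 4.8-5.1% at 0.05, whatever the split and whether or not treatment worked.

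**Its power.** The standard error of the difference between two subgroup effects with n1 and n2 per arm is 7√(2/n1 + 2/n2), on 2(n1 + n2) − 4 = 38 degrees of freedom. Suppose the effects truly differ by the full 4.7 kg:
- 11 / 10: standard error 4.33 kg, noncentrality 4.7 / 4.33 = 1.09, power 43% at alpha 0.20 and 19% at 0.05.
- 15 / 6: standard error 4.78 kg, noncentrality 0.98, power 39% and 16%.
- 17 / 4: standard error 5.50 kg, noncentrality 0.85, power 35% and 13%.

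**The case against.** The strongest reply is that the plan never says it will compare significance verdicts. Results by subgroup could be set side by side as estimates, and this is a 54-patient phase 2 trial in which no confirmatory claim or stopping decision rests on SAP 5.7. This stands as far as the rates are concerned. A reader might infer that the plan will report a false difference about half the time. The documents do not support that as a flat statement. It needs the verdict-comparison reading, a real effect near 4.7 kg, alpha 0.20 carried into the subgroups, two-level factors and splits like those assumed. With no treatment effect the figure is 32%.

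A reader might also infer that a spurious demographic difference would steer patient selection for the next trial. The documents do not say so: protocol section 3 (endpoint table) and 8.2.13 tie patient selection to MRI body composition, in 8.2.13 together with weight and HbA1c.

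It is also true that an interaction test here has little power. That argues for showing the estimate and its interval, not for doing without the comparison.

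The exploratory defence covers less. SAP 5.7 speaks of exploring the further factors, such as diabetic status and age. For gender, race and ethnicity it sets out to determine whether effects differ. Even under the side-by-side reading, no estimate of the difference or its uncertainty is planned.

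**Conclusion.** The point holds: both documents set a question about differences between subgroups, and the analyses they name do not answer it. That conclusion needs no assumption about numbers.

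The size is conditional. If a difference is read from discordant verdicts at two-sided alpha 0.20, with 21 evaluable per arm, a two-level factor and equal true effects, disagreement occurs in 48-57% of trials at 4.7 kg (splits 11 / 10 to 17 / 4), 43-44% at half that effect and 32% at none. The decision rule, the splits and the alpha are assumptions. The figures concern weight change only; secondary and safety measures were not computed. The change should be made, although the primary conclusion does not depend on it.

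**What to change.** Revise SAP 5.7 as follows.
- For weight change and the other continuous endpoints, fit one linear model (ANCOVA) per factor with a treatment-by-subgroup term. Report the interaction estimate with its confidence interval.
- For >5% weight loss and adverse events, report the risk difference in each subgroup and the difference between subgroups, with confidence intervals. Use exact or penalised methods where cells are sparse. Ordinary logistic regression with an interaction would be unstable in cells as small as 4 to 6 per arm.
- Show subgroup effects as estimates with intervals, make no within-subgroup significance claims, and label all of this exploratory.
- Name the levels of each factor and state the confidence level and any alpha for the interaction. At 0.20, each test still gives a false difference 20% of the time.
- State the limitation: about 39-43% power at alpha 0.20 (16-19% at 0.05) for splits from 11 / 10 to 15 / 6, even if effects differ by the full 4.7 kg, and less for more uneven splits. A null interaction must not be reported as evidence of equal effects.

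The cost is SAP wording and a little programming, with no new data or patients. SAP 1.0 gives the SAP precedence over the protocol's analysis plan; protocol 9.4.7 can be aligned at the next amendment.
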